APPENDIX 3. INHIBITORS AND INDUCERS OF CYP2C8

In addition to any medications listed in the Investigator's Brochure that are excluded from concomitant use, the following inhibitors and inducers of CYP2C8 should not be taken by patients receiving LIQ861:

CYP2C8 Inhibitors

- Gemfibrozil
- Ketoconazole
- Trimethoprim
- Clopidogrel
- Deferasirox
- Teriflunomide
- Telithromycin
- Phenelzine
- Montelukast
- Quercetin

CYP2C8 Inducers

- Rifampin

APPENDIX 4. PK SAMPLE COLLECTION, PROCESSING, AND SHIPMENT

Sample Collection and Processing

- One (1) 3 mL Vacutainer tube containing (K₂) EDTA (lavender-top blood collection tubes, 13 x 75 mm, BD Vacutainer catalog # 367856 or equivalent) will be collected for PK analysis at each of the time points specified in Section 6.4 of the protocol. Fill tube as completely as possible to ensure sufficient sample volume for the required tests.
- Immediately after the sample is drawn, gently invert the tube 5 to 10 times to thoroughly mix the anticoagulant and place the tube at room temperature. Samples can be stored at room temperature for up to 60 minutes prior to completing the processing procedure.
- Centrifuge the sample at room temperature at 2500 to 3000 rpm (approximately 650 to 1450 x g) for 10 to 15 minutes to achieve a clear plasma layer over the red cells. The speed and time may be varied according to the make and model of centrifuge used.
- Immediately transfer (approximately) equal portions of the plasma to two (2) properly labeled polypropylene sample storage tubes (Sarstedt 3.5 mL tubes, P/N 60.549 or equivalent), cap and freeze samples at -20°C until shipment.

Note: Use of gel separation blood collection tubes is not recommended for PK sample analysis, as drug may be absorbed by the barrier gel.

Sample Collection and Processing

- All sample shipments should be preceded by a phone call or fax prior to their receipt. All HIV positive or other known infectious sample shipments must be preceded by a phone call or facsimile prior to their receipt.
- Detailed sample inventory information must accompany the samples. Lack of paperwork or illegible information will delay sample login and project initiation. Samples that are unclearly or incompletely labeled may be subject to additional handling fees. Submission of sample inventory information in electronic form is encouraged.
- Frozen samples should be shipped via overnight courier with an adequate amount of dry ice Monday through Wednesday to the following:

ACM Global Laboratory
Attn: Clinical Trials Specimen Management
[name]
[name]

- Notify ACM by e-mail, facsimile, or telephone that a shipment is leaving your location. Upon arrival, the shipment will be unpacked and the contents verified and documented. If requested, the individual responsible at the shipment point of origin will be notified of sample disposition.
- Backup samples should be stored frozen at the Investigational site until successful receipt of initial shipment is confirmed by ACM.

APPENDIX 5. INHALATION DEVICE USER SURVEY

Inhalation Device User Survey

1. How long have you been using the RS00 Model 8 Dry Powder Inhaler (DPI) with LIQ861 (circle the most accurate)?

Less than 1 week	Less than 1 month	Less than 6 months	Less than 1 year	More than 1 year
---------------------	----------------------	-----------------------	---------------------	---------------------

2. How would you rate the RS00 Model 8 DPI compared to the Tyvaso Inhalation System you were previously using (circle 1)?

0 Strongly Prefer the Old Device	1 Prefer the Old Device	2 No Preference	3 Prefer the New Device	4 Strongly Prefer the New Device
--	----------------------------------	-----------------------	----------------------------------	--

For Investigational Site Personnel Only:
Site Number Patient ID Date Administered Investigator/Coordinator Initials

APPENDIX 6. ASSESSMENT OF HEPATIC AND RENAL IMPAIRMENT

Evidence of severe hepatic impairment will be assessed by simply documenting the patient's history or presence of ascites and encephalopathy. A patient will be considered to have severe hepatic impairment if the patient both:

- has evidence of ascites, AND
- has been diagnosed with or has evidence of encephalopathy grade of 1 or higher based on the West Haven Criteria.

Any patient fitting this profile should be excluded from the study.

Renal impairment will be assessed by calculating estimated glomerular filtration rate (eGFR) using Modification of Diet in Renal Disease (MDRD) equation ([CDEP 2010](#)):

$$\text{eGFR} = 175 \times (\text{Serum Creatinine})^{-1.154} \times (\text{Age})^{-0.203} \times (0.742, \text{if female}) \times (1.212, \text{if African American})$$

Where Serum Creatinine is measured in mg/dL, Age is measured in years, and eGFR is measured in mL/min/1.73m². Subjects with eGFR less than 45 will be excluded from the PK sub-study and subjects with eGFR of less than 30 will be excluded altogether.

APPENDIX 7. 6MWT INSTRUCTIONS AND WORKSHEET

The following instructions on performing a 6MWT are reproduced from the guidelines published by the American Thoracic Society ([ATS 2002](#)). A sample data collection worksheet and Borg Scale are provided at the end of the instructions ([below](#)).

Safety Considerations

Testing should be performed in a location where a rapid, appropriate response to an emergency is possible. The appropriate location of a crash cart should be determined by the physician supervising the facility.

Supplies that must be available include:

- oxygen,
- sublingual nitroglycerine,
- aspirin, and
- albuterol (metered dose inhaler or nebulizer).

A telephone or other means should be in place to enable a call for help.

The technician should be certified in cardiopulmonary resuscitation with a minimum of Basic Life Support by an American Health Association-approved cardiopulmonary resuscitation course. Advanced cardiac life support certification is desirable. Training, experience, and certification in related health care fields (registered nurse, registered respiratory therapist, certified pulmonary function technician, etc.) are also desirable. A certified individual should be readily available to respond if needed.

Physicians are not required to be present during all tests. The physician ordering the test or a supervising laboratory physician may decide whether physician attendance at a specific test is required.

If a patient is on chronic oxygen therapy, oxygen should be given at their standard rate or as directed by a physician or a protocol.

Reasons for immediately stopping a 6MWT include the following:

- chest pain,
- intolerable dyspnea,
- leg cramps,
- staggering,
- diaphoresis, and
- pale or ashen appearance.

Technicians must be trained to recognize these problems and the appropriate responses. If a test is stopped for any of these reasons, the patient should sit or lie supine as appropriate depending on the severity or the event and the technician's assessment of the severity of the event and the risk of syncope. The following should be obtained based on the judgment of the technician:

- blood pressure,
- pulse rate,
- oxygen saturation, and

- physician evaluation.

Oxygen should be administered as appropriate.

Technical Requirements and Equipment

The 6MWT should be performed indoors, along a long, flat, straight, enclosed corridor with a hard surface that is seldom traveled. The walking course must be 30 m in length; a 100-ft hallway is, therefore, required. The length of the corridor should be marked every 3 m. The turnaround points should be marked with a cone (such as an orange traffic cone). A starting line, which marks the beginning and end of each 60-m lap, should be marked on the floor using brightly colored tape.

The following equipment is required to conduct the assessment:

- Countdown timer (or stopwatch)
- Mechanical lap counter
- Two small cones to mark the turnaround points
- A chair that can be easily moved along the walking course
- Worksheets on a clipboard
- A source of oxygen
- Sphygmomanometer
- Telephone
- Automated electronic defibrillator

In preparation for the assessment, patients should:

- Wear comfortable clothing and appropriate shoes for walking,
- Use their usual walking aids, such as a cane or walker,
- Continue their usual medical regimen
- Not have exercised vigorously within 2 hours of the beginning of the test.

Additionally, a light meal is acceptable before early morning or early afternoon exams.

Instructions for Conducting the 6MWT

1. Repeat testing should be performed about the same time of day to minimize intraday variability.

A “warm-up” period before the test should not be performed.

The patient should sit at rest in a chair, located near the starting position, for at least 10 minutes before the test starts. During this time, check for contraindications, measure pulse and blood pressure, and make sure that clothing and shoes are appropriate. Complete the Patient Information portion of the data collection worksheet ([below](#)).

Pulse oximetry is optional. If it is performed, measure and record baseline heart rate and oxygen saturation (SpO₂) and follow manufacturer's instructions to maximize the signal and to minimize motion artifact. Make sure the readings are stable before recording. Note pulse regularity and whether the oximeter signal quality is acceptable.

- a. The SpO₂ should not be used for constant monitoring during the exercise. The technician must not walk with the patient to observe the SpO₂. If worn during the walk, the pulse oximeter must be lightweight (less than 2 pounds), battery powered, and held in place (perhaps by a “fanny pack”) so that the patient does not have to hold or stabilize it and so that stride is not affected.

Have the patient stand and rate their baseline dyspnea and overall fatigue using the Borg scale provided [below](#).

Set the lap counter to zero and the timer to 6 minutes. Assemble all necessary equipment (lap counter, timer, clipboard, Borg Scale, worksheet) and move to the starting point.

Instruct the patient as follows:

“The object of this test is to walk as far as possible for 6 minutes. You will walk back and forth in this hallway. Six minutes is a long time to walk, so you will be exerting yourself. You will probably get out of breath or become exhausted. You are permitted to slow down, to stop, and to rest as necessary. You may lean against the wall while resting, but resume walking as soon as you are able.

You will be walking back and forth around the cones. You should pivot briskly around the cones and continue back the other way without hesitation. Now I'm going to show you. Please watch the way I turn without hesitation.”

Demonstrate by walking one lap yourself. Walk and pivot around a cone briskly.

“Are you ready to do that? I am going to use this counter to keep track of the number of laps you complete. I will click it each time you turn around at this starting line. Remember that the object is to walk AS FAR AS POSSIBLE for 6 minutes, but don't run or jog.

Start now, or whenever you are ready.”

Position the patient at the starting line. You should also stand near the starting line during the test. Do not walk with the patient. As soon as the patient starts to walk, start the timer.

Do not talk to anyone during the walk. Use an even tone of voice when using the standard phrases of encouragement. Watch the patient. Do not get distracted and lose count of the laps. Each time the participant returns to the starting line, click the lap counter once (or mark the lap on the worksheet). Let the participant see you do it. Exaggerate the click using body language, like using a stopwatch at a race.

After the first minute, tell the patient the following (in even tones): “You are doing well. You have 5 minutes to go.”

When the timer shows 4 minutes remaining, tell the patient the following: “Keep up the good work. You have 4 minutes to go.”

When the timer shows 3 minutes remaining, tell the patient the following: “You are doing well. You are halfway done.”

When the timer shows 2 minutes remaining, tell the patient the following: “Keep up the good work. You have only 2 minutes left.”

When the timer shows only 1 minute remaining, tell the patient: “You are doing well. You have only 1 minute to go.”

Do not use other words of encouragement (or body language to speed up).

If the patient stops walking during the test and needs a rest, say this: “You can lean against the wall if you would like; then continue walking whenever you feel able.” Do not stop the timer. If the patient stops before the 6 minutes are up and refuses to continue (or you decide that they should not continue), wheel the chair over for the patient to sit on, discontinue the walk, and note on the worksheet the distance, the time stopped, and the reason for stopping prematurely.

When the timer is 15 seconds from completion, say this: “In a moment I'm going to tell you to stop. When I do, just stop right where you are and I will come to you.”

When the timer rings (or buzzes), say this: “Stop!” Walk over to the patient. Consider taking the chair if they look exhausted. Mark the spot where they stopped by placing a bean bag or a piece of tape on the floor.

When the timer is 15 seconds from completion, say this: “In a moment I'm going to tell you to stop. When I do, just stop right where you are and I will come to you.”

When the timer rings (or buzzes), say this: “Stop!” Walk over to the patient. Consider taking the chair if they look exhausted. Mark the spot where they stopped by placing a bean bag or a piece of tape on the floor.

After the test record the postwalk Borg dyspnea and fatigue levels and ask this: “What, if anything, kept you from walking farther?”

If using a pulse oximeter, measure SpO₂ and pulse rate from the oximeter and then remove the sensor.

Record the number of laps from the counter (or tick marks on the worksheet).

Record the additional distance covered (the number of meters in the final partial lap) using the markers on the wall as distance guides. Calculate the total distance walked, rounding to the nearest meter, and record it on the worksheet.

Congratulate the patient on good effort and offer a drink of water.

Data Collection Worksheet for Conducting a Six-Minute Walk Test

Lap Counter: -----	Date:
	Technician ID:
	Walk #:

Patient Information

Patient Information			
Patient Name:		Race:  White  Black or African American  Asian  Native Hawaiian or Other Pacific Islander  American Indian or Alaska Native	Medications Before Test (Medication, Dose, Time)
Patient ID #:			
Age:	_____ years		
Height:	_____ ft _____ in, _____ meters		
Weight:	_____ lbs, _____ kg		
Blood Pressure:	_____ / _____		

Test Information

Test Information					
	Baseline	End of Test	Stopped or Paused before 6 minutes?	 No	 Yes, Reason?
Time:	____:____	____:____			
Heart Rate:	____	____			
Dyspnea ^a :	____ (Borg)	____ (Borg)			
Fatigue ^b :	____ (Borg)	____ (Borg)			
SpO ₂ ^c :	____ %	____ %			
			Other symptoms at end of test?	 Angina	 Dizziness
				 Hip, Leg, or Calf Pain	 Other
					Lap Distance: ____ meters
					Total Laps: ____ laps
					Final Partial Lap: ____ meters
					6MWD ^d : ____ meters
					Predicted distance: ____ meters
					Percent predicted: ____ %

Technician Comments and Interpretation (including comparison with a pre-LIQ861 6MWD):

- a. The patient should rate baseline dyspnea using the Borg Scale (below). At the end of the test, the patient should be reminded of their baseline score before recording the End of Test score.
- b. The patient should rate baseline fatigue using the Borg Scale (below). At the end of the test, the patient should be reminded of their baseline score before recording the End of Test score.
- c. Collection of SpO₂ is optional. If recorded, the device must be lightweight (less than 2 lbs) and should not be continuously monitored.
- d. 6MWD = (Total Laps × Lap Distance) + Final Partial Lap

The Borg Scale

0	Nothing at All
0.5	Very, Very slight (just noticeable)
1	Very slight
2	Slight (light)
3	Moderate
4	Somewhat severe
5	Severe (heavy)
6	
7	Very Severe
8	
9	
10	Very, very severe (maximal)

1. GLOSSARY OF ABBREVIATIONS

Abbreviation	Description
6MWD	Six Minute Walk Distance
AE	Adverse Event
CSR	Clinical Study Report
DPI	Dry Powder Inhaler
ECG	Electrocardiogram
eCRF	Electronic Case Report Form
MedDRA	Medical Dictionary for Regulatory Activities
MITT	Modified Intent-to-Treat
MLWHF	Minnesota Living With Heart Failure
MMRM	Mixed Effect Model for Repeated Measures
NT-proBNP	N-Terminal Pro B-Type Natriuretic Peptide
NYHA	New York Health Association
PAH	Pulmonary Arterial Hypertension
PK	Pharmacokinetics
PT	Preferred Term
QID	“quater in die” – 4 Times a Day
SAP	Statistical Analysis Plan
SD	Standard Deviation
SE	Standard Error
SOC	System Organ Class
TEAE	Treatment Emergent Adverse Event
WHO	World Health Organization

2. INTRODUCTION

LIQ861 (treprostинil) inhalation powder is a prostacyclin vasodilator for the treatment of pulmonary arterial hypertension (PAH; World Health Organization [WHO] Group 1) in patients with New York Heart Association (NYHA) Class II-III symptoms, to improve exercise ability.

This statistical analysis plan (SAP) is developed based on Protocol Version 3.0 (dated 20th March 2019) and the electronic case report form (eCRF) dated 23rd July 2018. The purpose of this SAP is to ensure that the data listings, summary tables and figures which will be produced, and the statistical methodologies that will be used, are comprehensive and appropriate for the assessment of study objectives specified in the protocol. Any amendments to the SAP will be made prior to database lock. Any additional analyses not described in the final SAP or deviations from the final SAP will be documented in the clinical study report (CSR).

A CSR summarized data collected from Screening up through the Month 2 Visit in order to satisfy the agreement for the regulatory filing. An initial version of the SAP detailed the analyses required for that CSR. This SAP (Version 2.0) details the analyses required for the final reporting of the study.

2.1. RESPONSIBILITIES

Nuventra Pharma Sciences, Inc. will perform the statistical analyses and are responsible for the production and quality control of all tables, listings and figures.

3. STUDY OVERVIEW

3.1. STUDY OBJECTIVES

The primary objective of this study is to evaluate the long-term safety and tolerability of LIQ861 in patients with PAH.

The secondary objective of this study is to evaluate the comparative bioavailability of treprostинil between two formulations of inhaled therapy.

3.2. STUDY DESIGN

Study LTI-301 is a Phase 3, open-label, multicenter study in subjects with PAH to evaluate the long-term safety and tolerability of LIQ861. The study will evaluate the long-term safety and tolerability of LIQ861 in PAH patients who have been on stable doses of Tyvaso (treprostинil) inhalation solution for at least 3 months (“Transition” group) or who are taking no more than 2 approved non-prostacyclin oral PAH therapies (“Add-On” group). A subset of patients on Tyvaso (N=18) will be enrolled in a 1 directional crossover to compare the bioavailability and PK of treprostинil as they transition from Tyvaso to LIQ861.

For all subjects, scheduled study visits to the clinic will occur at Screening (within 28 days prior to Baseline on Day 1), Baseline (Day 1), Week 2, Month 1, Month 2, Month 4, and every 4 months thereafter (e.g., Month 8, Month 12) until termination of the study by the Sponsor, all subjects are transitioned to an extension study or regulatory approval.

Telephone contact to assess adverse events (AEs), concomitant medications, and PAH symptoms will be made every 4 months, beginning at Month 6 (e.g., Month 6, Month 10) until the Study Termination Visit.

Unscheduled visits may be conducted at the Investigator's discretion for subject safety monitoring, follow-up of AEs, or other reasons that will be documented.

Subjects that clinically worsen on open-label LIQ861, as determined by Investigator's discretion, may be withdrawn from the study and rescue therapy initiated per standard of care.

3.3. DETERMINATION OF SAMPLE SIZE

At least 130 PAH subjects were to be enrolled to ensure that at least 100 completed 2 months of treatment to evaluate the long-term safety and tolerability of LIQ861. The study enrolled 121 subjects and 113 had the Month 2 visit.

3.4. TREATMENT ASSIGNMENT AND BLINDING

All subjects will receive open label LIQ861 and doses according to their individualized titration.

3.5. ADMINISTRATION OF STUDY MEDICATION

Tyvaso Transition subjects will receive training on the use of the dry powder inhaler (DPI) device and then administer their first dose of LIQ861 at the investigational site at the Baseline Visit (Day 1) under the supervision of study staff and remain in the clinic for safety observation per Investigator discretion. The initial LIQ861 dose will be matched to the comparable prescribed Tyvaso dose at transition as detailed in the study protocol (Appendix 2 of the protocol); subsequently, LIQ861 will be maintained on a QID dosing schedule for the duration of the study. During this time, dose titration may be ordered at the Investigator's discretion.

Add-On subjects will receive training on the use of the DPI device and then administer their first dose of LIQ861 at the investigational site at the Baseline Visit (Day 1) under the supervision of study staff. Study drug will be administered for Add-On subjects initially at 25 mcg treprostinil in LIQ861 QID, with timing of dose titrations chosen at the Investigator's discretion while maintaining a QID dosing schedule. Alterations to the dosing interval (e.g. 3 times a day or 5 times a day) must be approved by the Sponsor.

Titration to a higher dose of treprostinil in LIQ861 will be governed by a subject's degree of symptomatic relief, not to tolerance of prostacyclin side effects. If there are no symptoms of prostacyclin excess, doses of LIQ861 will be increased in 25 mcg treprostinil strength increments in accordance with the Guidance for LIQ861 Dose Selection and Titration described in the study protocol (Appendix 2 of the protocol) up to the maximum allowed dose of 150 mcg treprostinil strength. Dosing in excess of 150 mcg treprostinil strength, which has not been previously studied, will require consent from the Sponsor.

Two LIQ861 formulations were used during the conduct of the LTI-301 study and, for brevity, are referred to as the “clinical formulation” and the intended “commercial formulation”.

Four dose strengths of LIQ861 were used in this study: 25, 50, 75, and 100 mcg treprostinil capsules. For dose levels in excess of 100 mcg treprostinil, 2 capsules of lower strength were used in immediate succession to achieve the desired dose of treprostinil.

It should be noted that when the study was ongoing, the strength of the intended commercial formulation was recalculated, resulting in revised capsule strengths of 26.5, 53, 79.5 and 106 mcg treprostinil. The clinical and intended commercial formulations have been determined to be comparable and clinical differences in strengths were expected to be negligible. For ease of review, the 25, 50, 75, and 100 mcg capsule strength nomenclature will be used throughout the tables, listings, and figures.

4. ENDPOINTS

4.1. PRIMARY ENDPOINT

The primary endpoint will be the incidence of Treatment-Emergent Adverse Events (TEAEs) and Serious Adverse Events grouped by Medical Dictionary for Regulatory Affairs (MedDRA) System Organ Class, dose level, time on drug, and relationship to dose-titration.

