3.2. Endpoints

3.2.1. Primary Endpoint

The primary endpoint will be the incidence of Treatment-Emergent Adverse Events (TEAEs) and Serious Adverse Events (SAEs) grouped by MedDRA System Organ Class, dose level, time on drug, and relationship to dose titration.

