6. GENERAL ASPECTS FOR STATISTICAL ANALYSIS

6.1. GENERAL METHODS

Subjects differ by treatment history prior to entry to Study LTI-301 - the two groups will be referred to as the Transition and Add-On Groups. For all summary tables data will be presented for all subjects (Overall) and by group.

Continuous variables will be summarized using the number of non-missing observations (n), mean, standard deviation (SD), standard error (SE), median, minimum and maximum. Categorical variables will be summarized using frequencies and percentages.

Categorical shift tables will include marginal totals.

Unless otherwise specified, the estimated mean and median for a set of values should be printed out to 1 more decimal place than the original values, and SD and SE should be printed out to 2 more decimal places than the original values. The minimum and maximum should report the same number of decimal places as the original values.

Percentages will be displayed with 1 decimal place; except percentages will not be presented when the count is zero and 100% will be presented as an integer. The number of subjects in the analysis population will be the denominator.

Unless stated otherwise, baseline will be taken as the last available non-missing assessment prior to study drug administration (Day 1).

In by-visit summary tables, the baseline will be summarized using all available data, but also for each visit using only the baseline data from subjects with available data at the visit; hence the mean change from baseline will equal the mean visit value – mean baseline value.

Throughout this document ‘change from baseline’ refers to the actual change from baseline (i.e. visit value – baseline value).

All data will be listed separately for each group. Data listings will present study days in addition to dates, where study day is derived as (assessment date – first day of dosing + 1).

Since there is no formal hypothesis testing, no adjustment for multiplicity will be made for inferential statistical comparisons within or between groups.

Programming of analyses, tables and listings will be performed using R Version 3.4.0 or higher (R Foundation for Statistical Computing, Vienna, Austria) or SAS® Version 9.3 or higher (Cary, North Carolina, US).

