7.2. DEMOGRAPHIC CHARACTERISTICS

These data were reported in the Month 2 clinical study report. The outputs will be repeated for this final study report.

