8.1. ADVERSE EVENTS

AEs will be coded using MedDRA version 20.1.

AEs will be considered TEAE unless there is clear indication that the event occurred prior to the first dose of study drug. AEs present prior to study drug administration that increased in severity or relationship to study drug afterwards will also be classed as TEAEs.

All AEs that occur after the first dose of study drug will be considered to be 'treatment-

'emergent' with the exception of AEs that occur more than 7 days after the last dose of study drug.

Events with missing or partial dates will be handled such that in the absence of contradictory information an AE is treatment emergent (see Section 6.2).

Only TEAEs will be included in the summary tables.

An overall summary will present the number of subjects with:

- any TEAE*
- any TEAE considered as related to study drug (evaluated by the investigator as Related or severity not reported)*
- any serious TEAE*
- any serious TEAE considered as related to study drug*
- Maximum severity TEAEs of mild, moderate or severe; i.e. a subject with TEAEs at different intensities will be summarized at the most severe intensity
- Maximum severity TEAEs considered as related to study drug of mild, moderate or severe; i.e. a subject with TEAEs at different intensities will be summarized at the most severe intensity
- any TEAE leading to study drug discontinuation (i.e. TEAEs reported as having either an action taken as 'Drug Withdrawn') and/or Study Discontinuation*
- any TEAE considered as related study drug discontinuation (i.e. TEAEs reported as having either an action taken as 'Drug Withdrawn') and/or Study Discontinuation *
- any TEAE leading to death*

The table will also include the total number of TEAEs reported for those flagged (*). The total number of unique terms within subjects will also be presented for those flagged (*), counting each TEAE PT only once within each subject.

This overall summary will be presented for both the Safety and mITT populations.

This summary will also be produced using the Safety population for the following:

- the subgroups in Section 6.3
- those TEAEs with an onset up to the Month 2 visit (inclusive) and those with an onset after the Month 2 visit separately.

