The number and percentage of subjects with TEAEs will be presented by system organ class (SOC) and PT for both the Safety and mITT populations. Subjects with multiple TEAEs within a SOC or SOC/PT combination will be counted only once for that SOC or SOC/PT combination.

A similar summary will be presented for the Safety population of TEAEs considered as study drug related.

The 'all causality' summary will also be produced using the Safety population for the following:

- the subgroups in Section 6.3
- those TEAEs with an onset up to the Month 2 visit (inclusive) and those with an onset after the Month 2 visit separately.

SOC and PT summaries of TEAEs by maximum severity (mild, moderate or severe) will be presented for all TEAEs and also for those considered as related to study drug.

All summaries will be ordered by descending frequency of total number of subjects within each SOC and then similarly by decreasing frequency of total number of subjects within each PT, in the overall column. In cases of SOCs or PTs with equal frequencies, AEs will be sorted alphabetically.

All TEAEs will be listed by subject and AE onset day. AE duration (stop date/time – start date/time) will be included in the listing; where applicable imputed data will be used for the calculation of AE duration, but the original date information will be presented in the listing.

The following separate listings will also be provided:

- serious AEs
- TEAEs leading to study drug discontinuation (i.e. TEAEs reported as having either an action taken as 'Drug Withdrawn') and/or Study Discontinuation

If there are any deaths a listing will include the date of death and the adverse event(s) associated with death.

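### SAP 8.1 does not tabulate the primary endpoint as defined: no TEAE or serious-TEAE table by LIQ861 dose level or by relationship to dose titration, and no System Organ Class table for serious TEAEs

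*SAP*

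**What the plan says.** SAP 4.1 groups TEAE and SAE incidence by "System Organ Class, dose level, time on drug, and relationship to dose-titration". Protocol 3.2.1 has the same four groupings: "grouped by MedDRA System Organ Class, dose level, time on drug, and relationship to dose titration". The Statistical Considerations part of the protocol synopsis also commits to showing AE frequencies by dose level.

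SAP 8.1 plans the following:

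- An overall summary with rows for any TEAE, related TEAEs, serious TEAEs, maximum severity, discontinuation and death. Selected rows also carry event totals, and "The total number of unique terms within subjects will also be presented for those flagged".
- SOC and preferred-term (PT) tables for all TEAEs, for related TEAEs and by maximum severity.
- Repeats of the overall summary and the all-causality SOC/PT table by the 6.3 subgroups, and for "those TEAEs with an onset up to the Month 2 visit (inclusive) and those with an onset after the Month 2 visit separately".
- Listings: "All TEAEs will be listed by subject and AE onset day", plus separate listings of serious AEs, of events leading to discontinuation and of any deaths.

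The columns come from SAP 6.1: "For all summary tables data will be presented for all subjects (Overall) and by group". The groups are Transition and Add-On. The 6.3 subgroups are age, sex, race, number of PAH medications and time since diagnosis. Events after the first dose are treatment-emergent "with the exception of AEs that occur more than 7 days after the last dose of study drug".

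**The concern.** In a descriptive safety study the tables are the result. If the planned tables omit a grouping that the primary endpoint names, the report does not deliver that endpoint, and a reader must rebuild the incidence from listings.

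The two groupings with no table at all are the ones tied to how the drug is given. Dosing is individually titrated in 25 mcg steps (SAP 3.5), so the Overall, Transition and Add-On columns pool subjects at different doses and at different times since a dose change. Neither document says how an event is assigned to a dose or what counts as related to titration. If those rules are chosen after the data are seen, they carry less weight than rules fixed before database lock.

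**Working it through.** The plan states no figure to reproduce here. The main check sets the endpoint against the planned outputs.

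**1. Coverage.** Two event types × four groupings = 8 combinations.

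| Grouping | TEAEs | Serious TEAEs |
|---|---|---|
| SOC | Planned (SOC/PT tables) | Absent: summary rows and a listing only |
| Time on drug | Planned (Month 2 split) | Planned (serious row of the overall summary, Month 2 split) |
| Dose level | Absent | Absent |
| Relationship to titration | Absent | Absent |

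Planned: 2 for TEAEs + 1 for serious TEAEs = 3. Absent: 8 − 3 = 5.

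**2. Search for the missing outputs elsewhere.** SAP 7.5 uses dose for exposure only: duration by dose, average daily dose, dose shifts, and dose against previous Tyvaso dose. SAP 8.2 to 9.6 contain no AE output. Protocol 8.7 promises descriptive summaries without naming tables.

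**3. After-Month-2 denominator.** SAP 6.1 makes the analysis population the denominator, which is 121 for the Safety Population (SAP 5.2), and 8.1 does not override it. SAP 3.3 says 113 subjects had the Month 2 visit. As a proxy for those still at risk, 113/121 = 0.934, so any after-Month-2 percentage would be about 6.6% too low in relative terms. With an assumed 60 affected subjects: 60/121 = 49.6%, against 60/113 = 53.1%. The proxy is imperfect, because a subject may miss the visit and stay on drug, or attend it and stop.

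**4. Missing classifications.** SAP 6.2.2 takes missing causality as related and missing severity as severe. The overall summary in 8.1 counts an event as related if the investigator said so or if its severity is missing. Read literally, an event judged unrelated but with no severity recorded would count as related, and one with no causality recorded would not. The two sections conflict.

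**5. Time at dose.** This matters for the fix. SAP 7.5 defines duration as last date − first date + 1 and summarizes it for each dose. Take an invented path: 50 mcg on Days 1–14, 75 mcg on Days 15–21, 50 mcg on Days 22–60. True time at 50 mcg is 14 + 39 = 53 days. The formula applied per dose gives 60 − 1 + 1 = 60. Adding 7 days at 75 mcg counts 67 days in a 60-day period.

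**6. Overlap of post-change time with early treatment.** Assume five increases (125/25 = 5) on Days 7, 14, 21, 28 and 35, each with a 7-day window. The windows cover 5 × 7 = 35 of the first 60 days (58%), against 7/60 = 12% after a single increase. All five windows end by Day 41, before Month 2, so splitting at Month 2 would not separate the two effects.

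**The case against.** The strongest reply is that little is lost. No hypothesis is tested (protocol 8.4), all TEAEs are listed by onset day, a Month 2 report already exists under an earlier SAP, and SAP section 2 allows further analyses to be documented in the CSR. The endpoint wording is also modest: it names SOC rather than PT, asks for incidence rather than rates, and does not require dose or titration to be crossed with SOC. With 121 subjects, heavily crossed tables would be thin.

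The last part stands and limits what should be asked for. The rest does not fill the gap:

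- A listing gives no incidence by dose.
- The Month 2 report may contain such tables, but it is not among the documents and cannot cover later events. Where Version 2.0 means to carry outputs forward it says so, as in SAP 7.2: "The outputs will be repeated for this final study report". Section 8.1 has no such statement.
- Permission to add analyses is not a plan to produce these.

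A reader might infer more than the documents support. Serious TEAEs are not untabulated: they are counted overall, by subgroup and on each side of Month 2. Time on drug is not missing. Nor do the documents show that the data go uncollected or that a dose effect is being hidden; they contain no event counts from which such an effect could be sized.

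**Conclusion.** The point holds and should be fixed before database lock. Under SAP Version 2.0 as written, five of the eight event-by-grouping combinations of the primary endpoint have no table. Dose level and relationship to titration are absent for both event types, and SOC is absent for serious TEAEs. No decision rule is affected. The consequence is that the final report would not give the primary endpoint as the SAP and protocol define it.

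The conclusion concerns the final report only and does not depend on what the Month 2 report contains. The denominator figure rests on 113 as a proxy for subjects at risk. The denominator and the causality clause are lesser defects in the same section and do not add to the count of five.

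**What to change.** In SAP 8.1:

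1. Add a serious-TEAE table by SOC, with PT optional.
2. Add a descriptive table of TEAEs and serious TEAEs by LIQ861 dose at onset, with the number of subjects exposed and the time at each dose as denominators. Sum separate spells at the same dose. Assign events in the 7 days after the last dose, and that time, to the last dose taken. State a rule for onset on a day of dose change. A SOC breakdown is optional where cells allow.
3. Add a descriptive table of TEAEs and serious TEAEs by onset within a pre-stated window after a dose change (for example 7 days) versus other treated time. Show the period after the first LIQ861 dose as its own category, because leaving it in the comparator would mix initiation effects into it. State which category takes precedence when a change falls in that period, since protocol Appendix 2 allows titration on Day 1. State also that post-change time overlaps early time on drug and that the comparison is not causal.
4. For the after-Month-2 tables, use as denominator the subjects still at risk after the cut under the SAP's own TEAE rule, not all 121. State a cut day for subjects without that visit.
5. In the definition of related TEAEs in the overall summary, refer to missing causality instead of missing severity, to agree with 6.2.2.

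If a grouping will not be tabulated, amend the endpoint or give the reason in 8.1.

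The cost is SAP wording and a few tables. The protocol has prescribed dose changes recorded at visits and phone calls (6.2.4 to 6.2.6.2) and dose adjustments at unscheduled contacts (6.3), and SAP 7.5 already needs duration by dose. It is an assumption that every between-visit change is dated. High-dose cells will be sparse: with zero events in n subjects, the one-sided 95% upper limit is 1 − 0.05^(1/n), which is 45% for n = 5, 26% for n = 10 and 14% for n = 20 (assumed cell sizes). Subjects who reach high doses are also selected for tolerance, which is a further reason to label the tables descriptive.
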